9.4 Phase 2 – Post-Therapy Monitoring Phase

After Phase 1, the COOLSTAT will be stopped by pressing the 'Start/Stop' button on the control panel of the device. Once the device is in the pause mode, the nasal mask will be removed from the subject and the temperature probe disconnected from the COOLSTAT, however, the hospital core temperature sensor will remain connected to the subject, or it can be replaced with the esophageal, SpotOn, or bladder sensor at the discretion of the PI. This will conclude any cooling with the COOLSTAT. Manual data collection will continue for two hours after COOLSTAT cooling has concluded to capture the subject's response post-cooling.

Any new cooling therapies can be applied to the subject as directed by clinicians, but will need to be noted in the case report forms. Phase 2 ends at the conclusion of this two-hour observational period. The COOLSTAT must be prepared for the next subject according to the procedures in Section 9.8.

9.5 Phase 3 - Post-Cooling Follow-up

For the next 22 hours, the subject's vital data will continue to be manually collected every 4 hours, and a qualified board-certified otolaryngologist or otolaryngology resident (under the supervision of a board-certified otolaryngologist) will perform a follow-up examination of the upper airways within 24 hours of the end of Phase 1 COOLSTAT Therapy. The intensivist will perform the post-therapy nasal exam if an otolaryngologist is not available.

9.6 Tasks during Cooling

Once the COOLSTAT cooling has commenced, data will be manually collected and recorded on the supplied Therapy and Observation Record (requirements are also listed in Section 12.7). Data collection activities will be performed throughout the therapy phase (Phase 1.) These activities will include:

- Note the time when collecting data during this time interval.
- Note and record blood pressure and ICP values, prior to starting COOLSTAT, as well as during its use and after it is turned off.
- Record any antipyretic or other medications given and its dose during this time interval.
- Record the subject's core and tympanic temperatures displayed on the CoolStat and hospital monitor.
- Assess and record the subjects' level of shivering according to the Bedside Shivering Assessment Scale (scale written on the Data Record).
- Record any anti-shivering actions taken during this time interval.
- Check that the nasal mask has not inadvertently shifted during the study, and readjust if necessary during Phase 1. Apply a small amount of Vaseline to nasal

pillows to facilitate a good seal to nostrils without needing to apply much pressure.

- Briefly remove the nasal mask every 4 hours to inspect for any sign of pressure ulcer. Reapply Vaseline to facilitate good seal between nasal pillows and nostrils.
- Check that the saline bag is periodically dripping to ensure it is supplying saline to the disposable set during Phase 1 and record.
 - If the saline bag is observed to have <500 mL of saline remaining, replace saline bag with 1L bag to ensure continuous availability of saline.
 - Note when a bag is replaced on the Data and Observation Record.
- Record the tracheal volumes of fluid collected in the canisters from the tracheal tube at COOLSTAT therapy initiation (Phase 0) and twice daily for the remainder of the study. Oral fluids should be suctioned into a third canister and should not be included in the fluid volume measurements.
- Record if there was any AE during this time interval (a separate AE form must be completed.)
- Per standard of care, verify correct positioning of the endotracheal tube and record (three times daily). Exam subject for abdominal distension and record every 8 hours.
- There is an increased risk of insensible losses during the cooling period. Clinical providers will be made aware of this and advised to take this into account as they monitor for possible dehydration and provide maintenance IV fluids for study participants. Clinical and study personnel will evaluate the patient for any signs of dehydration and record every 8 hours.
- Device alarms will be responded to as described during training and in the error table in the COOLSTAT Operator's Manual. An alarm for high relative humidity of air delivered to the patient is to be expected; it indicates that the desiccant cartridge needs to be changed according to instructions in the manual.

9.7 Anti-Shivering Regimen

Shivering during cooling increases oxygen consumption and generates heat that interferes with the cooling process. If the subject starts shivering, anti-shivering regimen will be performed following existing hospital routines. A shivering response due to the application of an active, external cooling system is not unexpected. Any anti-shivering protocol that is used will be documented in the subject's case forms. The subjects will be actively monitored for signs of shivering. The proactive use of prophylactic anti-shivering agents should not be used.

9.8 Turning Off and Clean-up

At the end of Phase 1, the COOLSTAT device will be turned off by pressing the 'Start/Stop' button. At this point, the nasal mask will be removed from the subject by loosening the head straps. The temperature connection to the COOLSTAT will be

removed from the device. The nasal mask component and the desiccant cartridge will be disposed of per standard hospital protocols. Specific steps are detailed below:

1. Power off COOLSTAT device using the power switch per Operator's Manual.
2. Disconnect the nasal mask component from the COOLSTAT and dispose of mask assembly.
3. Open device lid and remove and dispose of desiccant cartridge.
4. Remove saline bag from IV hanger, record the remaining amount of fluid in the bag, and dispose of the bag and any remaining saline per standard hospital protocols.
5. Wipe down external device surfaces with standard, hospital supplied wipes.
6. Return the device to the designated storage area (per study team personnel).

9.9 Subject Study Completion

The study Subject Completion Form section of the therapy case form is to be completed after 22 hours of additional follow-up (end of Phase 3).

10.0 Adverse Events, Warning, and Precautions

For this Feasibility IDE Clinical Trial, the definitions outlined in the FDA Guidance for Clinical Investigators, Sponsors, and IRBs, Adverse Event Reporting to IRBs - Improving Human Subject Protection (January 2009) will be applied to adverse events.

The investigational device exemption (IDE) regulations define an unanticipated adverse device effect (UADE) as "any serious adverse effect on health or safety or any life-threatening problem or death caused by, or associated with, a device, if that effect, problem, or death was not previously identified in nature, severity, or degree of incidence in the investigational plan or application (including a supplementary plan or application), or any other unanticipated serious problem associated with a device that relates to the rights, safety, or welfare of subjects" (21 CFR 812.3(s)). UADEs must be reported by the clinical investigator to the sponsor and the reviewing IRB, as described below:

- For device studies, investigators are required to submit a report of a UADE to the sponsor and the reviewing IRB as soon as possible, but in no event later than 10 working days after the investigator first learns of the event (§ 812.150(a)(1)).
- Sponsors must immediately conduct an evaluation of a UADE and must report the results of the evaluation to FDA, all reviewing IRBs, and participating investigators within 10 working days after the sponsor first receives notice of the effect (§§ 812.46(b), 812.150(b)(1)).

- The IDE regulations, therefore, require sponsors to submit reports to IRBs in a manner consistent with the recommendations made above for the reporting of unanticipated problems. Possible exceptions would include situations in which the specificity or severity of the event is not consistent with the description in the investigator's brochure, or it can be determined that the observed rate of occurrence for a serious, expected AE in the clinical trial represents a clinically important increase in the expected rate of occurrence.

To report an adverse event or unanticipated adverse device effect, the proximate investigator will complete an Adverse Event Form. All adverse events must be reported to the sponsor immediately (within 24 hours of becoming aware of the event). It is also the responsibility of the Principal Investigator to inform the representative of the center's IRB according to the IRB policies and procedures.

10.1 Adverse Event Definitions

On the Adverse Event Form, each adverse event will be classified as anticipated or unanticipated; device related or not device related; and classified as mild, moderate or severe. The severity classification will be determined by the investigator proximate to the event, who will use his or her clinical judgment and assign a severity classification based in the following definitions.

- **MILD** (resolved without intervention within study period)
- **MODERATE** (medical intervention required, not life threatening, did not alter study course)
- **SEVERE** (potentially life-threatening and required immediate intervention, could or has altered study)

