Hypothesis	
The primary hypothesis regarding cooling performance is that at least 75% of the subjects will reach normothermia (core temperature $\leq 37.5^{\circ}\text{C}$) within 4 hours of starting COOLSTAT cooling.
 
The primary hypothesis regarding temperature maintenance is that at least 75% of the subjects' core temperatures remain between 36°C and 37.5°C for 80% of the steady state² time following the initial achievement of 37.5°C.

Outcomes	
Performance Outcomes
 
 1) This feasibility study is intended to confirm that the COOLSTAT system can cool within expected performance parameters and can reach and maintain normothermic cooling therapy over the study period. Subjects are expected to reach normothermia (core temperature $< 37.5^{\circ}\text{C}$) within 4 hours of starting COOLSTAT cooling. Subject temperatures are expected to be maintained within a 1.5°C temperature band, between $36^{\circ}\text{C} - 37.5^{\circ}\text{C}$, for 80% of the steady state time following the initial achievement of 37.5°C.¹

¹ This recognizes that some subjects will have short periods of break-through fever over the course of the study.

² If a subject must be disconnected from the CoolStat device for transport from the NCCU to another unit (e.g., to radiology or angiography suite), they will be reconnected to the device at steady state if their core temperature

	
2) Data collected will help to confirm cooling models and the control system algorithm by examining subject cooling response as a function of air flow rate and properties of the air supplied to the subjects.
 
3) The study will demonstrate that the COOLSTAT System can perform in the clinical setting and identify possible human and equipment interface refinements.
 
Safety Outcomes
 
Safety will be assessed by the following:
 
 4) The incidence and severity of all adverse events (including, but not limited to serious adverse events and non-related adverse events). 5) Assessment as to any potential contribution to the adverse event that may be device related or related to transnasal cooling therapy. 
Secondary Outcomes
 
This study may provide insight into the incidence of shivering, although the study design is not sufficiently powered to expect definitive conclusions.

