5.0 Risk/Benefit Analysis

5.1 Analysis of Risks to Subjects and Potential Benefits

The risks to the subjects in this study are broken into risks of the COOLSTAT device and risks to the subject since they will not be receiving standard of care. Although summaries are provided below, detailed risk evaluations (e.g., hazards analyses and failure modes and effects) have been completed and are available as part of the IDE application.

The most significant risk mitigation is that throughout this study, the subject will be under regular clinical and study supervision and can be easily and quickly switched to the standard of care for cooling therapy if necessary.

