5.1.2 Risks Associated with Denying Standard of Care

The standard of care for febrile patients in the NCCU starts with antipyretic treatment (acetaminophen 650 – 1000 mg orally) once a fever is detected, as specified by a temperature $\geq 38.3^{\circ}\text{C}$ (measured via an embedded core sensor). After 1-2 hours, if the patient's temperature is still above this limit, a temperature modulating device (TMD) is initiated with appropriate anti shivering regimen. Throughout the time period a TMD is utilized, acetaminophen administration is continued (650 – 1000 mg orally every 6 hours).

For this study, the COOLSTAT will be initiated after approximately 1 or 2 hours of antipyretic administration (per institutional guidelines) and will replace the use of any other TMD. This is an investigational study which generally does not provide benefits to the subject above the standard of care. Anticipated advantages to using the COOLSTAT over traditional TMDs are listed in Section 5.5.1, but it is the goal of this study to start to assess the validity of these potential advantages. If at any point the subject is not cooling properly or is otherwise unsafe from the use of the COOLSTAT, the subject can be quickly and easily switched to the standard of care cooling treatment. Subject assessment at 4 hours and 8 hours will be conducted consistent with the current standard of care.

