9.3 Phase 1 – Active Cooling Phase

Subjects will receive COOLSTAT cooling treatment, with a maximum of 30 cmH₂O of air pressure (as automatically controlled by the device). The COOLSTAT will be operated in closed-loop control mode and will automatically modulate and control air flow and maintain the subject's core temperature between 36 °C and 37.5 °C, as measured by the esophageal, SpotOn, or bladder temperature sensor. The device will be set to target 36.5 °C.

The COOLSTAT will attempt to cool to and maintain this temperature range over the phase period. The core temperature will be recorded automatically by the COOLSTAT device, and is displayed on the COOLSTAT screen.

While the COOLSTAT is in use, no other cooling therapies will be used other than antipyretics.

Throughout Phase 1, the subject's temperature and vital signs will be monitored per NCCU protocol, as well as data collected in the CRFs. If any alarms occur, the appropriate action will be taken as described herein. COOLSTAT device errors will be addressed via an available trained technician and study team training (See Operator's Manual for a description of the possible device errors). Treatment may be discontinued at any time if adverse events are encountered or alternate cooling methods are required on an urgent basis. The Investigator or their designee must review any such emergency changes to therapy and complete an Adverse Event form detailing the reason for the change.

Per standard of care in the NCCU, maximum allowed limits will be imposed for a sustained increase in SBP >5 minutes above existing SBP threshold limits (specific to the indication being treated) despite standard of care intervention. In this event, COOLSTAT use will be discontinued for that subject. Once the COOLSTAT is discontinued due to SBP elevation, it will not be restarted for that subject. However, the study team will continue to monitor SBP to see if it recovers back to baseline value after the COOLSTAT is turned off. The Investigator or their designee must complete an Adverse Event form detailing the event and the value of the SBP prior to, during and after the COOLSTAT was used.

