13.3.2 Adverse Events

All adverse events will be analyzed to determine if the cause is from the COOLSTAT device or other related activities from the study protocol.

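### The adverse event form's two-way relatedness field does not match the cause analysis in 13.3.2, so protocol-caused events that are not clearly due to the device share a code with the underlying disease

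*Combined protocol and SAP*

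**What the plan says.** Section 10.1 describes what is recorded on the Adverse Event Form: anticipated or not, a severity grade, and "device related or not device related". It describes no other causality entry.

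Section 13.3.2, the adverse event part of the analysis plan, is a single sentence: "All adverse events will be analyzed to determine if the cause is from the COOLSTAT device or other related activities from the study protocol".

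Section 5.1 divides the risks of participation into "risks of the COOLSTAT device and risks to the subject since they will not be receiving standard of care". Section 5.1.2 is devoted to the second class and says that the study device "will replace the use of any other TMD". Section 9.3 adds that while the device runs "no other cooling therapies will be used other than antipyretics".

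The safety outcomes in the synopsis (section 1.0) ask whether an event may be "device related or related to transnasal cooling therapy". Other places word causality differently again, as set out below.

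**The concern.** The safety analysis asks a question that the recorded field, as described, cannot answer alone. The missing category covers a risk class that the protocol itself names.

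Attribution carries more weight here than in a controlled trial. The synopsis describes a prospective observational study with no comparison arm, so no between-group difference can reveal harm that individual assessments misattribute. Section 2.1 also says that fever can worsen brain injury. Harm from delayed effective cooling could therefore look like progression of the underlying disease, which is what it would be coded with. One decision uses attribution directly: under 6.10, the move from 8-hour to 24-hour cooling requires that no significant adverse event be attributed to the device.

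**Working it through.** No arithmetic applies to the plan's own figures. The check sets side by side every place that defines or uses adverse event causality.

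| Place | Causes distinguished |
|---|---|
| 10.1 (form) | device; not device |
| 13.3.2 (analysis) | device; other activities of the protocol; by implication, neither |
| Synopsis, Outcomes | device; transnasal cooling therapy |
| Synopsis, Statistical Methodology | the device's contribution only |
| 6.4 | the device's contribution; direct relation to transnasal cooling |
| 5.1 and 5.1.2 (risk discussion) | device; not receiving standard cooling |

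1. **Count the categories.** Section 13.3.2 needs at least three outcomes and the field in 10.1 has two, so two of the three must share a code. An event of the underlying disease is not device related. Neither is an event caused by a protocol activity other than the device. Those are the two that merge.

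2. **Look for the missing category elsewhere.** The synopsis and 6.4 add transnasal cooling, which sits close to the device. Neither adds other study procedures or replaced standard cooling. Sections 5.1 and 5.1.2 name the latter as a risk but set no rule for recording it.

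3. **Try examples.**
   - *Harm while standard cooling is delayed or replaced.* The split in 5.1 puts this outside device risk. An investigator could also call it device related because the device did not cool. The plan does not say which.
   - *The optional bolus before cooling (5.2, 9.2).* It is given because the study device is about to start, but it is a drug, and it has no relatedness category.
   - *The tympanic probe (5.1.1, 9.2).* It is placed for study safety monitoring and is not part of the device.

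4. **See what can be recovered.** Let T be all adverse events, D those coded device related, and S those caused by the study in any way. If coding is correct, the field gives only D ≤ S ≤ T. D and T can be reported. S, and the part of S outside the device, cannot be read from the field.

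5. **See who decides, and where it is written down.** The synopsis and 6.4 name the attending physician and the investigator as assessors, but for the contribution of the device or of transnasal cooling. Section 13.3.2 names no assessor, category or rule for other protocol causes. Section 6.7 allows up to four sites, so different local readings of the same two-way field are foreseeable.

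**The case against.** The case on the other side is substantial, and most of it limits the point without removing it.

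- **The form is not in the documents.** Section 12.1 says blank templates are provided, but they are not included, so the form might hold more than 10.1 describes. This stands: the point rests on 10.1's description.
- **A reader might infer that the 13.3.2 analysis is impossible.** The documents do not support that. The synopsis provides for medical record review after any adverse event and a table of onset, intervention and resolution. With 30 treated subjects, causes could be separated case by case. What is missing is a prospective record of the result under a defined category.
- **A reader might infer that protocol-caused harm drops out of the safety results.** It does not. The synopsis and 6.4 cover all adverse events, including those unrelated to the device. Nor do the documents define study-related harm as the device-related count.
- **Harm from failure to cool is partly captured.** Insufficient cooling is an anticipated event (10.4), harm from a technical device failure goes on the form (10.6), and an urgent change of therapy requires a form (9.3). Some of these events may be coded device related. No rule requires this, and none forbids it.
- **Some apparent examples do not belong.** Harm from the mask fits device related, since the mask is part of the system. Core temperature probes are standard sensors at the sites (3.2).
- **Judgement remains.** Without a comparison arm, separating delayed-cooling harm from the brain injury is a clinical judgement whatever the form offers. A third category does not make that judgement certain. It does make it explicit and consistent.

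**Conclusion.** The mismatch between 10.1 and 13.3.2 is real and should be corrected. As described, the relatedness field cannot separate protocol-caused events that are not clearly due to the device from events of the underlying disease. The result is a loss of attribution and not of events.

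No size can be put on it. A reader might take the planning proportions in 6.6 (90% assumed, 75% lowest acceptable) and infer that 10% to 25% of subjects suffer harm that is misfiled. That does not follow. Those proportions concern subjects who do not reach 37.5 °C. They are neither a rate of adverse events nor a rate of miscoding. Such a subject need not be febrile either, since fever is defined as 38.3 °C or above. The 4-hour assessment is not a fixed exposure, because 9.3 allows treatment to stop earlier or continue longer.

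The conclusion assumes that the form carries no causality entry beyond the one in 10.1, and that 13.3.2 is meant to distinguish the device from other protocol activities, as its wording indicates.

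**What to change.** In 10.1, replace the two-way field with three categories:

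- (a) related to the device or to transnasal airflow or cooling;
- (b) related to another study procedure, or to replaced or delayed standard cooling;
- (c) unrelated to the study.

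Use the same three categories in the synopsis (Outcomes and Statistical Methodology), 6.4 and 13.3.2. Tabulate adverse events by them, showing (a), (b) and (a)+(b).

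The cost is one case report form field and one table column. The count of study-related events may look slightly less favourable than a device-related count alone. No treatment or stopping rule changes.

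### The three severity grades in section 10.1 are not exhaustive, so some events, including some that stop therapy, fit no grade and may be graded differently between sites

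*Combined protocol and SAP*

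**What the plan says.** Section 10.1 (Adverse Event Definitions) says each event is to be assessed for anticipation and device-relatedness "and classified as mild, moderate or severe". The grade is set by the investigator closest to the event, "who will use his or her clinical judgment and assign a severity classification based in the following definitions". There are three grades:

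- The lowest grade, MILD, is worded as "resolved without intervention within study period".
- The middle grade, MODERATE, is worded as "medical intervention required, not life threatening, did not alter study course".
- The highest grade, SEVERE, is worded as "potentially life-threatening and required immediate intervention, could or has altered study".

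Section 9.3 (Active Cooling Phase) plans for systolic pressure or ICP that stays above the institutional limit for more than 5 minutes despite standard care. For each it says: "In this event, COOLSTAT use will be discontinued for that subject". The device is not restarted, and an Adverse Event form must be completed, so a severity grade is required.

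Section 10.5 lists as serious any uncontrolled epistaxis that requires therapy to be stopped or an intervention. Section 10.9 foresees events still unresolved when the subject ends the study and follows them for at most another 24 hours.

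Section 1.0 (Outcomes) names as a safety outcome "The incidence and severity of all adverse events"; section 6.4 repeats it.

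**The concern.** Each definition combines several conditions, and the conditions differ from grade to grade. MODERATE combines clinical severity with an effect on the study. MILD combines absence of treatment with the timing of resolution. SEVERE combines threat to life with urgency of treatment. Grades built this way cover every event only by luck, and here they do not.

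At stake is a named safety outcome in a study whose purpose is safety and performance. If an event fits no grade, the investigator has to move it up or down, and the protocol gives no tie-break rule. Section 6.7 allows up to four sites, so like events may be tabulated under different grades.

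The section 10.5 list also uses the word severe, for nasal and oral mucosal ulceration, without saying whether it means the 10.1 grade. Serious events trigger a DSMB meeting (sections 1.0 and 14.5) and count in the flow-rate escalation rule for subjects 21 to 30 (section 13.0). Unclear grading could therefore reach beyond a table.

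**Working it through.** The plan gives no figure to reproduce here. The check is whether the definitions cover every case.

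**Inputs.** Section 10.1 uses four yes/no attributes: intervention required (I), potentially life-threatening (L), study course altered (A), resolved within the study period (R). That gives 2 × 2 × 2 × 2 = 16 combinations.

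**Rules as written.**

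- MILD: not I, and R
- MODERATE: I, not L, not A
- SEVERE: L and I. This is a generous reading: A is accepted either way, and any intervention counts as immediate.

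**Result.**

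| Combination | Count | Grade |
|---|---|---|
| No intervention, resolved (any L, any A) | 4 | MILD |
| No intervention, unresolved (any L, any A) | 4 | none |
| Intervention, not L, not A (any R) | 2 | MODERATE |
| Intervention, not L, A (any R) | 2 | none |
| Intervention, L (any A, any R) | 4 | SEVERE |

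Ungraded: 4 + 2 = 6 of 16. These are logical cases, not event frequencies; the documents give no event rates.

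Two further faults follow from the same rules. MILD does not mention threat to life, so a potentially life-threatening event that resolves untreated is graded MILD. If *immediate* is taken literally, a potentially life-threatening event that needs intervention, but not at once, has no grade either.

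**First gap: events that stop therapy.** Take the section 9.3 pressure or ICP event. Intervention has been given and COOLSTAT is permanently stopped. The other two attributes are left to the investigator:

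| Judged potentially life-threatening? | Stopping COOLSTAT alters study course? | Grade |
|---|---|---|
| Yes | either | SEVERE |
| No | No (follow-up continues) | MODERATE |
| No | Yes | none |

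One event can thus have three outcomes. The same holds for epistaxis that is treated, stops therapy and is judged not life-threatening: it is on the section 10.5 serious list, yet may have no severity grade.

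**Second gap: untreated and unresolved.** Phases 2 and 3 last 2 + 22 = 24 hours, and the post-therapy nasal exam may take place at any time within 24 hours of the end of cooling (sections 9.5 and 13.3.1). An untreated finding first seen late in that window may not resolve within the study period. Section 10.9 expects such cases. Even if its extra 24 hours were counted as study period, an event unresolved after that would remain ungraded.

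**The word severe in section 10.5.** Section 10.5 has a separate entry for any other potentially life-threatening event needing immediate intervention, which nearly repeats the 10.1 definition of SEVERE. If severe ulceration carried the 10.1 meaning, the two ulceration entries would add almost nothing to that one. Either reading is possible, and the documents do not choose.

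**After the change proposed below.** With two attributes there are 2 × 2 = 4 combinations: not I and not L is MILD; I and not L is MODERATE; L, with or without I, is SEVERE. All 4 receive exactly one grade.

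**The case against.** A reader might infer that the planned pressure and ICP events are exactly the ones that fall in the gap and so must be mis-graded. The documents do not support that. They never say these events are not life-threatening. SEVERE asks only for a potential threat, which an investigator may well see in a rise that persists despite treatment in a ventilated neuro-ICU patient. Nor do they say that stopping the device alters the study course: monitoring and data collection continue (sections 9.3 and 14.3), so MODERATE is arguable. What stands is that the grade depends on an undefined term and an individual judgement. The clinical-judgement clause does not repair this, because it binds the judgement to the same definitions.

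It would also be too strong to call these the key device-related events. Sections 5.1.1 and 6.9 expect no such pressure or ICP response, and relatedness is classified separately.

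A further objection is that no decision uses the grade. The move to 24-hour cooling uses attributed SAEs and a direct pressure criterion (section 6.10), flow escalation uses the 10.5 list, and the AE table shows intervention and resolution whatever the grade. This largely stands and limits the harm. It is not complete, because two entries in 10.5 depend on the word severe.

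Finally, one might size the problem as 1/20 = 5 percentage points per mis-graded subject in the double-nostril group and 1/10 = 10 points in the single-nostril group. That is true of any misclassified subject in groups of that size and says nothing particular about this fault.

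**Conclusion.** The point holds as a defect in a stated rule; section 10.1 is wrong as written. Every event must receive one of three grades, and 6 of 16 attribute combinations receive none, even with SEVERE read generously. The untreated, unresolved gap is plain on the text and is anticipated by section 10.9. The therapy-stopping gap rests on two assumptions: that the event is judged not potentially life-threatening, and that stopping COOLSTAT counts as altering the study course. Where either fails, the event has a grade, but sites may still disagree on which.

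The consequence is inconsistent grading between investigators and an unreliable severity tabulation for a named safety outcome. Sample size, power and both primary performance criteria are untouched. How often the gaps would be met cannot be estimated from the documents.

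**What to change.** Define the grades in section 10.1 on two attributes only:

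- MILD: no intervention required and not potentially life-threatening
- MODERATE: intervention required, not potentially life-threatening
- SEVERE: potentially life-threatening

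Remove from the grades every reference to resolution, the study period, the study course and immediacy of intervention. Deleting only the study-period words from MILD would not be enough: while MILD still requires resolution, an untreated and unresolved event has no grade.

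Record resolution and effect on therapy as separate fields. The AE table planned in section 1.0 (Statistical Methodology) already lists resolution, intervention and whether the patient continued in the study. That last column should make clear whether COOLSTAT itself was stopped, since follow-up continues after stopping.

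State whether severe in section 10.5 means the 10.1 grade, and reconcile the two sections. None of this changes a stopping rule, and no view is taken on those rules.

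The cost is an edit to 10.1, 10.5 and the Adverse Event form, with the usual amendment approval, and re-grading of events already recorded. The form is not among the documents, so it is an assumption that the form or source records hold enough to re-grade every past event.
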